APPENDIX 4: PROTOCOL AMENDMENT SUMMARY OF CHANGES

Appendix 4: Protocol Amendment 1 Summary of Changes

In addition to the changes listed below, this amendment includes administrative changes for consistency of language and changes to the Synopsis for consistency with the changes outlined below.

- Updated Version number, Date, and Amendment
- Signatory updated from [REDACTED]
- Protocol Synopsis:
 - Study phase updated to 2a correcting typographical error
 - Study Population: Exclusion criterion 12: removed ‘each’ as multiple vaccinations is not applicable
 - Study Drug Dosage and Administration: Removed reference to 2 injection vaccinations and added 30 minute observation period following vaccination
 - Rationale for Dose and Schedule Selection: updated for single dose regimen based on study results observed in ARCT-021-01 Parent Study
 - Adjustment of Dose: removed reference to stopping rules for subsequent doses as it is no longer applicable
 - Study Visit Schedule and Procedures: removed reference to two injection cohort as it is no longer applicable
 - Study Visit Schedule and Procedures: clarified definition of subjects receiving ARCT-021 vs receiving no injection
 - Study Visit Schedule and Procedures: clarified window for recording AEs in symptom diary
 - Primary Endpoint: provided additional details to primary endpoint for clarity
 - Statistical Considerations: Safety and Tolerability – included collection of any CESI, NOCDs following completion of Parent Study and Screening visit of this study
- Glossary
 - Added ‘MAAE’ and ‘NOCD’
 - Clarified definition of ‘enrolled’
- Section 1.2.1: provided additional details to primary endpoint to clarify major safety categories for analysis and to remove minor endpoints that fall under these categories
- Section 2.1: updated current status of approved vaccine availability
- Section 2.3: updated dosing rationale and revised dose regimen to single dose of 7.5 ug based on study results observed in ARCT-021-01 Parent Study
- Section 3.2, 8.3: updated study design to remove reference to 2 injection cohort and added precautionary safety measures including a post-dose observation period
- Section 3.5: clarified number of study centers

- Section 3.7, 3.8.2, 3.8.3: removed reference to subjects receiving 2 injections as it no longer applies
- Section 3.8.1: added definition of screen failure
- Section 3.8.2: reduced observation period from 1 hour to 30 minutes based on standardization of safety procedures across studies
- Section 5.2: Exclusion criterion 12 - removed 'each' as multiple vaccinations is not applicable
- Section 6.2 and 6.2.1: Clarified the collection of SAEs, NOCDs, CESIs and MAAEs and local and systemic solicited AEs
- Section 8.2: clarified use of study drug must be within 6 hour of first puncture of the drug vial
- Section 8.2: removed non-applicable dose levels (1.0, 3.0 and 5.0 µg) from Table 4
- Section 8.6: clarified stopping rules for treatment are no longer applicable for single dose administration resulting in the removal of sections 8.6.1, 8.6.2, 8.6.3
- Section 8.9.1: Disallowed Concomitant Therapy streamlined to focus on relevant therapies that may interfere with the evaluation of safety and immunogenicity and to remove unnecessary restrictions in a Phase 2 study
- Section 9.3.4: Addition of New Onset Chronic Disease (NOCD)
- Section 9.3.7: clarified Clinical Events of Special Interest definition
- Section 9.4.1: added duration for follow up of SAE to resolution for clarity
- Section 9.4.3: clarified reporting window for non-serious AEs
- Section 9.4.4.6: Sponsor Follow up updated to include CESIs and remove follow up of pregnancy cases which are addressed in section 9.5.4.
- Section 9.5.4: clarified pregnancy reporting and follow up for female subjects or partners of male subjects who received ARCT-021 only
- Section 9.5.5: clarified reporting requirements for CESIs
- Section 10.2, 10.3: added Immunogenicity population definition and elaborated on analyses plans; added Table 5: Grouping of Cohorts and Timepoints Across Studies ARCT-021-01 and ARCT-021-02 for Analysis
- Section 10.5.3: Safety analysis section updated to clarify the process for evaluating participants who received ARCT-021 vaccine in either the Parent study or in this study.
- Section 10.5.4: Immunogenicity Analyses updated to clarify the evaluation of participants who received ARCT-021 vaccine in either the Parent study or in this study.
- Section 10.5.5. added CESI analyses
- Appendix 1: Schedule of Assessments

- Screening: updated footnotes to include body systems for full physical exam, Immunogenicity sample and recording of SAE, CESI, NOCD and MAAE for clarification
- Subjects Not Receiving an Injection: removed measurement of body weight after Screening visit and clarified collection of SAE, CESI, NOCD and MAAE
- Subjects Receiving a Single Injection of ARCT-021 in This Study: corrected Week 13 to Week 9, removed measurement of body weight after Screening visit, clarified collection of SAE, CESI, NOCD and MAAE
- Removed schedule of assessment for ‘Subjects Receiving Two Injections of ARCT-021 in This Study as it is no longer applicable
- For subjects receiving ARCT-021 injection, added:
 - HbA1c and Coagulation at Day 1
 - Lymphatic exam to abbreviated physical exam
- Appendix 2: List of Laboratory Analytes – updated to confirm which analytes are included in cell mediated immunity tests.
- Appendix 4: Summary of Protocol Changes added for Amendment 1

8.1.4	Serious Adverse Events	23
8.1.5	Medically Attended Adverse Events (MAAE)	24
8.1.6	New Onset of Chronic Disease	24
8.1.7	AE Leading to Discontinuation/Withdrawal	24
8.1.8	Clinical Events of Special Interest	25
8.1.9	Adverse Event Summary :	25
8.1.9.1	Unsolicited Adverse Event Summaries.....	25
8.1.9.2	Solicited Events with Onset Within 7 Days of Injection	27
8.1.9.3	Adverse Events After Off-Study Vaccine.	28
8.2	CLINICAL LABORATORY ASSESSMENTS	29
9.	REFERENCES.....	30
10.	APPENDICES.....	31
10.1	APPENDIX A: SCHEDULE OF ASSESSMENTS	31
10.2	APPENDIX B: LIST OF LABORATORY ANALYTES	36

LIST OF ABBREVIATIONS

%GCV	Percent geometric coefficient of variation
AE	Adverse event
ANSI	American National Standards Institute
AQL	Acceptable Quality Level
CDA	Clinical Data Associate
CESI	Clinical Event of Special Interest
CTCAE	Common Terminology Criteria for Adverse Events
CRF	Case Report Forms
ECG	Electrocardiogram
EDC	Electronic Data Capture
GMFR	Geometric Mean Fold Rise
GMT	Geometric Mean Titer
IA	Interim Analysis
ICH	International Conference on Harmonisation
MedDRA	Medical Dictionary for Regulatory Activities
PRNT	Plaque reduction neutralization test
PT	Preferred Term
QC	Quality Control
SAE	Serious Adverse event
SAP	Statistical Analysis Plan
SOC	System Organ Class
SRC	Safety Review Committee
TEAE	Treatment emergent adverse event
WHO	World Health Organization

SAP REVISIONS

Version 1.0 of the IA SAP was finalized looking forward to having Database Soft-locked. Due to times constrain, not all data queries could be closed on time and the analysis will precede with a data cutoff with a few queries still open.

Protocol Version #	SAP Section	Modification	Description and Rationale
2.0	5.1	
 • Data is to be pulled when there are a few queries still open 	Updated to match real process
2.0	5	
 • Include definition of Seropositive 	Definition was missing, and it was updated by Sponsor via e-mail.

1. INTRODUCTION

This is a Statistical Analysis Plan for an Interim Analysis of Arcturus Therapeutics, Inc.'s study protocol ARCT-021-02 titled "A Phase 2a, Open Label Extension Study to Assess the Safety and Long-Term Immunogenicity of ARCT-021". See the protocol for additional details.

This SAP is based on protocol version 2.0 and provides details of the statistical analyses specified in the study protocol.

This study will be conducted in compliance with the study protocol and analyses will be conducted in compliance with ICH guideline E9 (Statistical Principles for Clinical Trials 1998), as applicable.

2. OBJECTIVES AND ENDPOINTS

NOTE: only the primary and secondary objectives and endpoints are to be evaluated at this interim analysis. The exploratory analysis of cell mediated immune responses is not being conducted at this time.

2.1 Objectives

2.1.1 Primary Objective

The primary objective is to assess the safety and reactogenicity of ARCT-021.

2.1.2 Secondary Objectives

Assessment of long-term neutralising antibody and anti-spike protein IgG responses following vaccination with ARCT-021.

2.1.3 Exploratory Objective

Assessment of cell-mediated immune responses following vaccination with ARCT-021

2.2 Endpoints

2.2.1 Primary Endpoint

The safety and reactogenicity of ARCT-021 will be assessed by determining the incidence, severity, and dose-relationship of solicited local and systemic adverse events, unsolicited adverse events (including serious adverse events (SAEs)), and changes in Laboratory Toxicity Results.

2.2.2 Secondary Endpoints

Immunogenicity

1. Mean and geometric mean titer or concentration (GMT, GMC) and the geometric mean fold rise (GMFR) in SARS-CoV-2 neutralizing antibodies and in binding antibody against the SARS-CoV-2 Spike glycoprotein and against receptor binding domain of the SARS-CoV-2 spike glycoprotein, at multiple time points in each cohort.
2. Proportion of ARCT-021-naïve participants (Cohort 1a; see Section 5.2 for description of cohorts)

seroconverting for neutralizing antibodies and binding antibodies against the SARS-CoV-2 Spike glycoprotein and against receptor binding domain of the SARS-CoV-2 spike glycoprotein will be assessed at multiple time points.

The proportion of ARCT-021 boosted participants (Cohort 1b) seroconverting for neutralizing antibodies and binding antibodies against the SARS-CoV-2 Spike glycoprotein and against receptor binding domain of the SARS-CoV-2 spike glycoprotein will also be assessed at multiple time points. This is an additional analysis to those specified in the protocol.

3. INVESTIGATIONAL PLAN

3.1 Study Design

Open label study enrolling healthy adult participants that participated in Study ARCT-021-01 (the Parent Study). Participants will enter this study approximately 3 months after their final study visit in the Parent Study. Participants will be followed up for a period of at least 12 months after the last injection of ARCT-021.

If all participants that were treated in the Parent Study consent to enroll in this study and meet the eligibility criteria, then 106 participants will be enrolled.

For participants who received an off-study vaccine, Safety and Immunogenicity reports will be censored at date of first dose of off-study vaccine. Any AE that occurs after off-Study vaccine will be reported separately.

3.2 Treatment

This is an open label non-randomized study. Participants who received placebo and participants who received a single injection of ARCT-021 in the Parent Study and are seronegative for SARS-CoV-2 PRNT50 neutralizing antibodies at screening will receive ARCT-021 in this study at a 7.5 µg dose level.

[figure not shown]
Participants who received two injections of ARCT-021 in the Parent Study and participants who received a single injection of ARCT-021 but are seropositive for SARS-CoV-2 PRNT50 neutralizing antibodies at screening will not receive any further injections of ARCT-021 in this study.

The duration of participation is designed such that all participants will be followed up until at least 12 months after their last injection of ARCT-021, irrespective of whether the last injection was in the Parent Study or in this study.

[figure not shown]
For participants receiving a single injection of ARCT-021, the study comprises an up-to-4-week Screening Period, a 1-day Study vaccine Administration Period and a 12-month Post Treatment observation period. The length of each participant's participation is approximately 13 months from screening to last study visit.

For participants who are not receiving ARCT-021 in this study, the study comprises an up to a 4-week Screening Period followed by a 9-month observation period. The length of each participant's participation is approximately 10 months from screening to last study visit.

STUDY DESIGN AND TREATMENT SCHEMA FOR PARTICIPANTS RECEIVING A SINGLE INJECTION OF ARCT-021

STUDY DESIGN AND TREATMENT SCHEMA FOR PARTICIPANTS NOT RECEIVING ARCT-021

4. CHANGES TO PLANNED ANALYSIS

This is an unplanned interim analysis that was not anticipated at the time of study initiation and is being conducted to support a regulatory filing in [REDACTED] and other jurisdictions, as applicable. In addition, based on data availability in specific subgroups of participants in this study, further adjustments in the original protocol-specified analyses are made. These additional changes from the analyses described in the protocol are summarized below.

4.1 Changes to Cohort Nomenclature

The sub-cohort nomenclature will be modified for Cohort 1b and Cohort 2 in this SAP as shown in Section 5.2 to allow ease of interpretation of data.

4.2 Changes to Calculation of Day Since Study Day 1

Table 5 (which describes ‘Grouping of Cohorts and Timepoints Across Studies ARCT-021-01 and ARCT-021-02 for Analysis’) in Protocol Version 2.0 is modified to reflect the revised Cohort naming convention described above. The revised table is shown in Table 1:

Table 1: Grouping of Cohorts and Timepoints Across Studies ARCT-021-01 and ARCT-021-02 for Interim Analysis #1

Approximate timing:	Duration of Follow-up After Last Vaccination				
	15 days	1 month	2 months	6 months	12 months
Cohorts 1a and 1b	Day 15 in ARCT-021-02	Day 29 in ARCT-021-02	Day 57 in ARCT-021-02	Day 169 in ARCT-021-02	Day 365 in ARCT-021-02
Cohorts 2(A) to 2(D2)	Day 15 in ARCT-021-01	Day 29 in ARCT-021-01	Day 57 in ARCT-021-01	Day 29 in ARCT-021-02*	Day 197 in ARCT-021-02*
Cohorts 2(E) to 2(H)	Day 15 in ARCT-021-01	Day 29 in ARCT-021-01	Day 57 in ARCT-021-01	Day 29 in ARCT-021-01*	Day 197 in ARCT-021-02*

1 Month = 28 Days

*Follow-up Day in Study ARCT-021-02 is based on nominal day since Day 1 in Study ARCT-021-01. For Cohorts 2 (A to D2) the time enrolled in the Parent Study is 57 days and the time between Parent Study and Day 1 in Study ARCT-021-02 is nominally 90 Days. Therefore, Day 1 in Study ARCT-021-02 is $57 + 90 = 147$ days after Day 1 in the Parent Study. For Cohorts 2 (E to H), the time enrolled in the Parent Study is 85 days and the time between Parent Study and Day 1 in Study ARCT-021-02 is nominally 90 Days. Therefore, Day 1 in Study ARCT-021-02 is $85 + 90 = 175$ days after Day 1 in the Parent Study

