Table 5: Grouping of Cohorts and Timepoints Across Studies ARCT-021-01 and ARCT-021-02 for Analysis

	15 days	1 month	2 months	6 months	12 months
Cohorts 1a and 1b (single dose of 7.5 µg in this Study)	Day 15 in ARCT-021-02	Day 29 in ARCT-021-02	Day 57 in ARCT-021-02	Day 169 in ARCT-021-02	Day 365 in ARCT-021-02
Cohort 2a (single dose of 7.5 µg in Parent Study only)	Day 15 in ARCT-021-01	Day 29 in ARCT-021-01	Day 57 in ARCT-021-01	Day 29 in ARCT-021-02	Day 197 in ARCT-021-02
Cohort 2b (single dose of 10 µg in Parent Study only)	Day 15 in ARCT-021-01	Day 29 in ARCT-021-01	Day 57 in ARCT-021-01	Day 29 in ARCT-021-02	Day 197 in ARCT-021-02
Cohort 2c (alternate single dose schedules in Parent Study only)	Day 15 in ARCT-021-01	Day 29 in ARCT-021-01	Day 57 in ARCT-021-01	Day 29 in ARCT-021-02	Day 197 in ARCT-021-02
Cohort 2d (alternate two dose schedules in Parent Study only)	Day 43 in ARCT-021-01	Day 57 in ARCT-021-01	Day 85 in ARCT-021-01	Day 29 in ARCT-021-02	Day 197 in ARCT-021-02

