- For participants in Cohort 2, immunogenicity data from the Parent Study for tests using the same assays as being performed in ARCT-021-02 is available only for participants in Cohorts 2 (D1), 2 (D2), 2 (E) and 2 (G). For these participants the Parent Study data will be presented together with the data from Day 29 in Study ARCT-021-2 (Day 29 is the only time point for which data is available for these cohorts in ARCT-021-02). For the remaining participants in Cohort 2 only data from Day 29 in Study ARCT-021-02 will be presented, as this is the only data (from the relevant assays) available at the time of this interim.

Table 2: Immunogenicity Data to be Included in Interim Analysis #1

Study/Time Point	Cohort/Sub-Cohort								
	1a	1b (A/C)	1b (B)	1b(D1/D2)	2 (A/C)	2 (B)	2 (D1/D2)	2 (E/G)	2 (F/H)
Parent Study									
Day 1	NA	NA	NA	X	NA	NA	X	X	X
Day 29	NA	NA	NA	X	NA	X	X	NA	X
Day 43	NA	NA	NA	X	NA	NA	X	X	X
Day 57	NA	NA	X	X	NA	NA	X	X	X
Day 85	NA	NA	NA	NA	NA	NA	NA	X	X
ARCT-021-02									
Day 1	X	X	X	X	NA	NA	NA	NA	NA
Day 29	X	X	X	X	X	X	X	X	X
Day 57	X	X	X	X	NA	NA	NA	NA	NA

NA = Not available/not applicable

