7.2 Secondary Immunogenicity Endpoints and Analyses

As per scheduled assessment, Cohort 1 will be reported at Study Day 29, Study Day 57, Study Day 169 and Study Day 365/Early termination, however only immunogenicity data up to ARCT-021-02 Day 57 will be available at the time of this interim. Cohort 2 will be reported at Study Day 29 (6 months FU), Study Day 197(12 Months FU) and Study Day 281 (15 Month FU)/Early Termination, however only immunogenicity data up to ARCT-021-02 Day 29 will be available at the time of this interim.

1. Mean and geometric mean titer or concentration (GMT, GMC) and the geometric mean fold rise (GMFR) in SARS-CoV- 2 neutralising antibody titer and IgG antibodies against the full-length SARS-CoV-2 recombinant spike protein antigen, RBD and N-antigen at multiple time points in each cohort.

Assessment of the long-term neutralising and anti-spike glycoprotein responses, including seroconversion rates, following vaccination with ARCT-021 is the secondary objective of the study. The study endpoint for these analyses include:

Assays:

- Neutralising antibody responses: pseudovirus neutralization test

- Binding antibody responses: Total IgG against the full-length SARS-CoV-2 recombinant spike protein, RBD and N-antigen will be assessed using a Meso-Scale Discovery (MSD) multiplex technology.

Endpoints at this interim:

- Cohort 1: Neutralising and binding antibody responses at Day 1, Day 29 (1 month after last dose of ARCT-021), Day 57 (2 months after last dose of ARCT-021)
- Cohort 2: Neutralising and binding antibody responses at ARCT-021-02 Day 29 (6 months after last dose of ARCT-021), which is Day 176 for Cohort 2 (A to D2) and Day 204 for Cohort 2 (E to H)

Descriptive statistics, by assessment time point, will be used to describe all immunogenicity results.

Mean and geometric mean titer (GMT) and geometric mean fold rise (GMFR) will be calculated for each cohort/sub-cohort (Section 5.2) in the Immunogenicity analysis population. The %GCV, median, standard deviation, minimum, and maximum values will also be displayed.

The GMT will be calculated as:

$$\text{GMT} = \text{anti-log}_{10} (\text{mean} [\log_{10} Y_i])$$

The GMFR will be calculated as:

$$\text{GMFR} = \text{anti-log}_{10} (\text{mean} [\log_{10} Y_i / B_i])$$

where Y_i is the post dose assay result for participant i ; and B_i is the baseline assay result for participant i . The exact 95% CIs will be provided for both GMT and GMFR.

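### SAP Table 1 maps the two-dose cohorts 2(E) to 2(H) to the wrong visits in four of five cells: three repeat single-dose days and the six-month cell names the wrong study

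*SAP*

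**What the plan says.** SAP Section 4.2 replaces protocol Table 5 with SAP Table 1. It explains that Table 5 "is modified to reflect the revised Cohort naming convention described above" and gives no other reason. The columns of Table 1 stand under the heading "Duration of Follow-up After Last Vaccination".

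For the two-dose parent cohorts E, F, G and H, called Cohort 2d in the protocol, the first cell of protocol Table 5 is "Day 43 in ARCT-021-01". Days 57 and 85 of the parent study follow, then Days 29 and 197 of ARCT-021-02. In SAP Table 1 the row "Cohorts 2(E) to 2(H" gives parent Days 15, 29 and 57, then "Day 29 in ARCT-021-01" with an asterisk, then Day 197 of ARCT-021-02.

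Three other places in the SAP bear on this:

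- Section 5.2 still groups assessments across the two studies by time since the last dose.
- Section 7.2 sets the Cohort 2 endpoint at this interim as "responses at ARCT-021-02 Day 29 (6 months after last dose of ARCT-021" and applies it to E to H as well as to A to D2.
- Table 2 plans parent Days 43, 57 and 85 for E/G, marks parent Day 29 as not available for them, and has no Day 15 row.

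**The concern.** The three early cells are identical to those of the single-dose row above. For a two-dose cohort those days run from the first injection, although the columns count from the last. The 6-month cell puts a parent-study visit where an extension-study visit belongs, and its asterisk leads to a footnote about follow-up days in ARCT-021-02.

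Table 1 is the only table in the SAP that defines the grouping by time since last dose, and persistence of the antibody response is the secondary objective. A programmer who followed the table would place two-dose results in the wrong column or in none. Double programming would not necessarily catch this, because both programmers would work from the same table. The interim analysis is meant to support a regulatory filing.

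**Working it through.** **The SAP's own figures.** The Table 1 footnote places Day 1 of the extension at 57 + 90 = 147 days (A to D2) and 85 + 90 = 175 days (E to H) after parent Day 1. Both sums reproduce, so the fault lies in the cells and not in this arithmetic.

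**Day of dose 2.** Neither document states it for the parent study. Each early cell of protocol Table 5 implies the same day: 43 - 14 = 29, 57 - 28 = 29, 85 - 56 = 29. The footnote agrees. It says "For Cohorts 2 (E to H), the time enrolled in the Parent Study is 85 days", against 57 days for A to D2, and 85 - 57 = 28, so dose 2 falls on Day 1 + 28 = Day 29.

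**Extension visits on the parent clock, E to H.** SAP Table 3 labels extension Day 29 as Day 203. Extension Day 197 is then 175 + 196 = Day 371.

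**Comparison for E to H**, with days after last dose = parent-clock day - 29:

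| Column | Protocol Table 5 | SAP Table 1 | Protocol, days after last dose | SAP, days after last dose |
|---|---|---|---|---|
| 15 days | parent Day 43 | parent Day 15 | 43 - 29 = +14 | 15 - 29 = -14 |
| 1 month | parent Day 57 | parent Day 29 | 57 - 29 = +28 | 29 - 29 = 0 |
| 2 months | parent Day 85 | parent Day 57 | 85 - 29 = +56 | 57 - 29 = +28 |
| 6 months | extension Day 29 | parent Day 29 | 203 - 29 = +174 | 29 - 29 = 0 |
| 12 months | extension Day 197 | extension Day 197 | 371 - 29 = +342 | +342 |

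SAP 7.2 counts extension Day 29 as Day 204 instead of 203. On that count the last two protocol values become 175 and 343, which changes nothing here.

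**Single-dose cohorts A to D2**, last dose on parent Day 1: 15 - 1 = 14, 29 - 1 = 28, 57 - 1 = 56, 175 - 1 = 174, and 147 + 196 - 1 = 342. The protocol row for E to H matches these in every column. The SAP row matches only at 12 months.

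**Effect at this interim, E/G.** Table 2 plans four visits after dose 2: parent Days 43, 57 and 85, and extension Day 29. Read against SAP Table 1:

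- The 15-day column is empty, because Table 2 has no Day 15 row.
- The 1-month and 6-month columns are empty, because both point to parent Day 29, which is not available.
- The 2-month column holds Day 57, which is 28 days after dose 2.

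Three of the four visits have no column and the fourth is in the wrong one.

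**Effect at this interim, F/H.** Table 2 marks parent data as available, but the text above it says such data are "available only for participants in Cohorts 2 (D1), 2 (D2), 2 (E) and 2 (G". If Table 2 is right, the parent Day 29 value appears under both 1 month and 6 months. If the text is right, the only F/H visit is extension Day 29, and it has no column.

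**The case against.** The strongest reply is that little depends on Table 1. SAP 5.3.2 reports immunogenicity by nominal visit day, with the labels of Table 3. SAP 7.2 names the six-month visit correctly. The safety windows in Section 8 do not use these columns, and no output with columns headed 15 days to 12 months is specified. The analysis is descriptive, and the intended visits can be recovered from Table 2 and Section 7.2. All of this stands and limits the harm. It does not make the table right, because Section 5.2 still calls for grouping by time since last dose and only Table 1 says how.

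A second reply is that the change may be deliberate. Section 4 lists changes to the planned analysis, the title of 4.2 speaks of days since Study Day 1, and the footnote counts from Day 1 of the parent study. A first-dose clock could account for the three early cells. It cannot account for the 6-month cell, where parent Day 29 would be both 1 month and 6 months. It also conflicts with the column heading, with Section 5.2 and with the stated reason of renaming.

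Two narrower points are fair. At this interim the 15-day column would be empty for the single-dose cohorts too, so no comparison between cohorts is lost there. And Table 2 is imperfect support: it conflicts with its own text for 2(B), where it marks parent Day 29 as available, as well as for F/H, and cells may have shifted in reading the PDF. The contradiction between Table 1 and protocol Table 5 does not rest on Table 2.

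**Conclusion.** The concern holds. Four of the five cells for Cohorts 2(E) to 2(H) contradict protocol Table 5 without a stated reason, and the 6-month cell is wrong on either clock. That finding needs no assumption.

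The size of the shift assumes dose 2 on parent Day 29. On that basis the early cells are misplaced by 28 days each (+14 to -14, +28 to 0, +56 to +28), and the 6-month cell by about 174 days. The consequences for individual E/G and F/H columns rest further on Table 2 as extracted. Mislabelling of two-dose results is possible but not certain, since the nominal visit labels would still show the true visit. The table should be corrected because it is the SAP's stated mapping and the correction is nearly free.

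**What to change.** Restore the 2(E) to 2(H) row of SAP Table 1 to the protocol Table 5 mapping: parent Days 43, 57 and 85, then ARCT-021-02 Days 29 and 197. Check that any program grouping results by time since last dose uses these visits. Reconcile SAP Table 2 with the text above it on which Cohort 2 parent-study data are available, for F/H and also for 2(B). The nominal labels in SAP Table 3 need no change for this point.

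The cost is four cells, a check of one mapping step and one clarification of data availability. No new data are needed. SAP 5.1 bars changes once the data are pulled, so this belongs before the pull. If that date has passed, the corrected mapping can be described and justified in the clinical study report, as protocol Section 10 provides for changes to SAP methods.
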